## 12.6 Additional Analysis

### 12.6.1 Treatment Satisfaction Analyses

Investigator's global satisfaction with sarecycline treatment will be analyzed using data at Week 12 from a single question: "how satisfied are you with sarecycline treatment outcomes", with response options ranging from 'Very Satisfied' to 'Very Dissatisfied'. Frequency of responses will be tallied for all Subjects. Proportion of Subjects for whom Investigators indicated 'Very Satisfied' or 'Satisfied' will be reported.

The analyses will be done for the overall cohort, using FAS, and stratified by age and other relevant subgroups. Relationship between Investigator satisfaction and subject characteristics will be explored using descriptive analyses.

### 12.6.2 Treatment Compliance

Compliance will be assessed by comparing the expected number of doses taken, based on the total number of treatment days between the encounters/surveys and within the entire treatment period of the study, with the number of unused doses/tablets identified/returned at each encounter/visit. Treatment compliance will be calculated for each subject/visit and over all visits for the Safety population. Compliance values that are less than 0% will be set to 0%. Summaries will be presented using descriptive statistics for the Safety population.

$$\text{Compliance} = [\# \text{ Expected to be used} - \# \text{ Unused}] / [\# \text{ Expected to be used}]$$

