## 5 STUDY MEDICATION

The study protocol will require identification and selection of patients considered as candidates for a specific medication, namely, sarecycline (Seysara®), as part of usual care. In this context, the study medication will be sarecycline (Seysara®). Site Investigators shall provide the commercial supply of sarecycline (Seysara®) to eligible study Subjects.

Sarecycline has a restricted market access in the U.S, with payers reimbursing for the commercial prescriptions on a restricted basis. Selection of only the patients who are able to fill the prescription for reimbursed sarecycline may not be representative of individuals who might be candidates for sarecycline in the U.S; this may impact the generalization of the study results. To avoid this potential selection bias and improve the prospect of generalization of study results, the commercial supply of sarecycline (Seysara®) will be supplied to Site Investigators for the study duration of 12 weeks.

Per FDA prescribing information, the recommended dosage of sarecycline is once daily with or without food:

- 60 mg for patients who weigh 33-54 kg,
- 100 mg for patients who weigh 55-84 kg,
- 150 mg for patients who weigh 85-136 kg. approximately 1.5 mg/kg once daily

The Site Investigators will prescribe relevant sarecycline dose to patients per their clinical judgement. Correspondingly, sarecycline prescribed dose at the start of the study and any subsequent modifications to dose during the study observation period will be captured as part of study data collection.

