## 17.1 APPENDIX A: Study Schedule of Events

Study Encounter (physical or virtual)	Baseline E1	E2	E3	End of Study E4	Early Termination Visit
Week †		Wk 4 (± 4 d)	Wk 8 (± 4 d)	Wk 12 (± 4 d)	-
Informed consent	X				
Selection criteria	X				
Demographics & baseline clinical characteristics 	X				
Physical examination 	X			X	X
AV medical history and relevant comorbidites 	X			X	X
Seysara dose 	X	X	X	X	X
Dispensing and return of study medication	X	X	X	X	X
Prior acne medication (since diagnosis & past 6 months)	X				
Concomitant general medication	X			X	X
Concomitant anti acne medication	X			X	X
Site Investigator's clinical assessment of acne 	X	X	X	X	X
Study subject questionnaires 	X	X	X	X	X
AEs/SAEs 	X	X	X	X	X
Reasons for premature study withdrawal					X

† Expected in-person or virtual encounter/visit schedule, in relation to the index date (date of first administration of sarecycline).

 Clinical characteristics data assessed retrospectively based on what is documented in patient medical charts.

 Routine physical examination conducted as part of usual care alone and as documented in patient medical charts; such data may include - blood pressure, waist circumference, height/weight measurements.

 May include AV date of diagnosis, baseline severity, relevant comorbidities, per clinician judgment and/or as documented in patient medical charts immediately before the index date; new emerging comorbidities during the study period will be recorded, based on the documentation in patient medical charts.

 Expected usage is once daily, every day during the duration of the trial.

 Site Investigator assessments of AV severity of Subjects may be conducted during subject visit to clinician offices, or via remote/virtual (telehealth) visits owing to Covid-related travel restrictions.

 Subject self-assessments will include PtGA of acne severity; various HRQOL assessments will be conducted at baseline and Week 12.

 In the case of premature study discontinuation due to an AE, the Investigator should make every effort to collect the AE duration and outcome. Any SAE that is ongoing at the End of the Study or at the time of premature withdrawal will be followed up until the SAE is resolved or at least up to 4 weeks. AE follow-up information will be reported in the eDCF.

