### 6.6.2 Treatment Compliance

Compliance will be assessed by comparing the expected number of tablets taken, based on the total number of treatment days between the encounters/surveys, with the number of used tablets identified/returned at each encounter/visit.

- The number of tablets expected to be taken/used for a specific treatment period between study encounters is calculated based on the number of treatment days in that period; if the

number of days is greater than 30, it will be set to 30, corresponding to the # of tablets in a single Seysara® bottle supplied to subjects during each study encounter/visit.

- The number of pills used for a specific treatment period between study encounters is calculated as a difference between 30 (maximum # of tablets in a Seysara® bottle dispensed for each study encounter) and # of unused/returned pills (by subject) at the following study encounter.

Compliance (%) for a given treatment/encounter period =  
[# of pills expected to be used - # of pills unused] \* 100 / [# of pills expected to be used]

Treatment compliance will be calculated for each subject/visit and over all study encounters/visits for the Safety population, as indicated above. For the overall compliance for each subject, average (mean) of % compliance at individual subject encounters/visits will be calculated.

Compliance values that are less than 0% will be set to 0%, and compliance values that are greater than 100% will be set to 100%. For Subjects with missing data, no missing data imputation will be performed, and the compliance statistics will be computed using non-missing values for the study cohort at relevant study timepoints.

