**Table 7.2.5. Seysara Treatment Characteristics**

Character	Baseline (N=x)	Week 4 (N=x)	Week 8 (N=x)	Week 12 (N=x)
Prescription dose	(M12.1)	(P13A1)	(P13A1)	(P13A1)
60 mg	n (%)	n (%)	n (%)	n (%)
100 mg	n (%)	n (%)	n (%)	n (%)
150 mg	n (%)	n (%)	n (%)	n (%)
Prescription frequency	(M12.2)	(P14A1)	(P14A1)	(P14A1)
Once daily	n (%)	n (%)	n (%)	n (%)
Other 1	n (%)	n (%)	n (%)	n (%)
Other 2	n (%)	n (%)	n (%)	n (%)

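### SAP 6.6.2 counts one tablet per day from a single 30-tablet bottle for every patient, so recorded changes of frequency or mid-interval strength can make full adherence look like poor compliance

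*Protocol*

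**What the plan says.** Protocol 12.6.2 defines the comparison: "Compliance will be assessed by comparing the expected number of doses taken, based on the total number of treatment days between the encounters/surveys". Its formula is expected minus unused, divided by expected. It does not mention a bottle size. Appendix A, footnote 4 (identical in both documents) supplies the daily rate: "Expected usage is once daily, every day during the duration of the trial".

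The operative rule is in SAP 6.6.2:

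- The expected count follows the length of the interval alone, at one tablet for each day on treatment.
- There is an upper limit: when the "number of days is greater than 30, it will be set to 30, corresponding to the # of tablets in a single Seysara® bottle".
- Tablets used are the "difference between 30 (maximum # of tablets in a Seysara® bottle dispensed for each study encounter" and the tablets returned.
- Compliance for an interval is 100 × (expected − unused)/expected, truncated to 0–100%. A patient's overall value is the mean of the interval percentages.

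The note to Table 7.4.2 repeats the 30-minus-returned rule. Table 7.4.3 repeats the compliance formula and refers to Section 6.6.2 for the expected count.

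The study also expects that prescriptions may vary. Protocol 5 says that "any subsequent modifications to dose during the study observation period will be captured". Protocol 7.3 to 7.5 ask at Weeks 4, 8 and 12 about dose modifications in the preceding four weeks. Table 7.2.5 tabulates strength and "Prescription frequency" at every encounter, with two rows for frequencies other than once daily.

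Protocol 8.5 and SAP 5.5 describe compliance differently, as used/expected against the assigned regimen.

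**The concern.** The expected count depends on days alone and the dispensed count is fixed at 30. Neither responds to the prescription. A patient told to take fewer tablets returns more of them, and the formula reads those as missed doses. None of the three strengths (60, 100, 150 mg) is a whole multiple of another, so a change between visits plausibly means a second bottle. The formula would then set two bottles' leftovers against one bottle's expected use.

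Patients misclassified this way are those whose prescription was altered, so the error need not be random. It would distort Table 7.4.3. It would also distort Table 7.4.2, which equates treatment days with tablets used and states no truncation. Adherence would be distorted as a covariate if Protocol 12.3.3 is carried out.

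**Working it through.** The plan states no compliance figure to reproduce, so the check applies its rule to patients who take every prescribed tablet.

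**Inputs.** Expected E = min(days, 30), 30 tablets per bottle, compliance = 100 × (E − unused)/E truncated to 0–100% (SAP 6.6.2). Visits are 4 weeks apart, ±4 days (Protocol 7), so the first interval is 24 to 32 days and later ones 20 to 36. The particular frequencies, and what happens to supply at a mid-interval change, are assumptions.

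**28-day interval, full adherence.**

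| Case | Unused | SAP 6.6.2 score |
|---|---|---|
| Once daily, no change | 30 − 28 = 2 | (28 − 2)/28 = 92.9% |
| Strength changed at a visit | 2 | 92.9% |
| Every other day | 30 − 14 = 16 | (28 − 16)/28 = 42.9% |
| Three times weekly | 30 − 12 = 18 | (28 − 18)/28 = 35.7% |
| Twice daily, two bottles | 60 − 56 = 4 | (28 − 4)/28 = 85.7% |
| Twice daily, one bottle (runs out at day 15) | 0 | 100% |
| Strength changed mid-interval, both bottles counted | 60 − 28 = 32 | (28 − 32)/28 = −14.3%, set to 0% |
| Same, old bottle only, change on day 3 / 14 / 26 | 27 / 16 / 4 | 3.6% / 42.9% / 85.7% |

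**Separating this from the surplus tablets.** The unchanged once-daily patient scores 92.9% only because the two surplus tablets are subtracted. That is a different defect. Using (30 − unused)/E removes it: once daily becomes 28/28 = 100%. Every other day is still 14/28 = 50%, and the mid-interval change is (30 − 32)/28 = −7.1%, set to 0%. The problem here therefore survives that correction.

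**Other interval lengths.** Every other day scores 0% (20 days), 25% (24), 50% (30), 53.3% (32) and 60% (36). The mid-interval change with both bottles counted scores 0% up to 30 days, 6.7% at 32 and 20% at 36.

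**Patient's overall value, one affected 28-day interval of three.** Strength change: (0 + 92.9 + 92.9)/3 = 61.9%. Every other day: (42.9 + 92.9 + 92.9)/3 = 76.2%. An unaffected patient has 92.9%.

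**Cohort mean.** The affected share is not given. Against an unaffected 92.9%, each 1% of patients affected in a 28-day interval lowers that interval's mean by 0.50 points (0.01 × (92.9 − 42.9)) to 0.93 points (0.01 × 92.9). The mean of overall values falls by 0.17 to 0.31 points, a third of that.

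**Table 7.4.2.** For 28 days on treatment, every other day is credited 30 − 16 = 14 days. The two-bottle case is credited 30 − 32 = −2 days.

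**The case against.** The case against has several strong parts.

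- **Once daily is the stated expectation.** Protocol 5 lists each strength as once daily and Appendix A agrees. The other-frequency rows in Table 7.2.5 are empty shell rows and do not show that anyone was dosed that way.
- **Resupply is not described.** Protocol 7.3 to 7.5 have one bottle per interval, exchanged at visits. A second bottle mid-interval, with both sets of leftovers summed, is an inference.
- **The use is descriptive.** Compliance is neither an endpoint nor a subgroup factor. Protocol 12.3.3 adjusts for adherence only where feasible, and the SAP specifies no multivariate model.
- **Actual programming is uncertain.** Table 7.4.3 subtracts variables it does not define, so some adjustment there cannot be excluded.

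All four limit the size of the point. A reader might infer that any fully adherent patient with a changed prescription scores 0% to 50%, and the documents do not support that. A strength change at a visit leaves the score where it was. Twice daily over 28 days scores 86% to 100%. Counting only one bottle gives up to 86% in the cases shown.

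What stands is that SAP 6.6.2 is a complete rule. Applied literally to a prescription that the SAP's own table provides for, it gives a wrong result. It also departs from the regimen-based, used/expected definition in Protocol 8.5 and SAP 5.5.

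**Conclusion.** The point holds, with limits. For a fully adherent patient in an affected 28-day interval, SAP 6.6.2 gives about 43% for every-other-day dosing (50% by used/expected). It can give as little as 0% for a mid-interval strength change. The first figure rests on an assumed frequency. The second rests on an assumed second bottle with both bottles' leftovers counted. These are interval values; with one such interval of three, the overall mean is about 62% to 76%, against 92.9% for an unaffected patient.

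The number of patients affected is unknown, so no cohort-level bias can be stated beyond the per-1% figures above. The tables at risk are 7.4.3 and 7.4.2. A reader might infer that the study's outcome analyses are biased through adherence. That would follow only if the Protocol 12.3.3 modelling is done, and the SAP does not plan it.

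**What to change.** In SAP 6.6.2, and correspondingly in Protocol 12.6.2, define for each interval:

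- **Expected** = tablets prescribed over the interval, from the recorded frequency and changes. The cap at 30 becomes a cap at the tablets actually dispensed.
- **Used** = all tablets dispensed minus all returned, across bottles and strengths.
- **Compliance** = 100 × used/expected, as Protocol 8.5 and SAP 5.5 already describe.

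Check over 28 days: every other day (30 − 16)/14 = 100%; mid-interval strength change (60 − 32)/28 = 100%; once daily (30 − 2)/28 = 100%.

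The documents do not show that the date of a dose change is collected. State a convention for when a change took effect if its date is missing, and report how many intervals rely on it. Use the same used-tablet count in Table 7.4.2, and do not equate tablets with treatment days for non-daily frequencies. Define the variables in Table 7.4.3. Reconcile Appendix A, footnote 4, with the frequency rows of Table 7.2.5; this review takes no position on the regimen.

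The cost is SAP wording, a matching protocol clarification and a small programming change. Strength and frequency are already tabulated, and dispensing and return are scheduled at each encounter. The added work is the date convention and confirming that any extra bottles were logged.

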### 12.6.3 Comparison of Investigator and Subject Assessment of AV Severity

The IGA and Subject perception of AV severity at Week 12 will be compared and reported using descriptive statistics, to portray the level of concordance/discordance in stakeholder perceptions. This analysis will be conducted for the entire cohort and for select subgroups. Correspondingly, the Investigator and Subject responses to the questions related to AV severity at baseline will also be compared and reported using descriptive statistics. The baseline level of

concordance/discordance between the stakeholders may be used to further stratify the Week 12 data analyses.

#### **12.6.4 CFB in PROs**

CFB in ASIS domain scores and subscale scores at Week 12 will be assessed. CFB will be first analyzed descriptively for the entire cohort and select subgroups. Analyses will be provided for FAS. For this analysis, the domain scores will be considered as continuous variables. No missing data imputation will be used. Scoring, scaling, and the handling of missing data will be handled in accordance with the recommendations accompanying the ASIS documentation and will be described in more detail in the SAP.

CFB in select individual items of ASIS, most specifically, items # 9 & 10, will be conducted by treating these variables as continuous variables. Based on data availability, CFB at Weeks 4 & 8 will be assessed in addition to Week 12. CFB will be first analyzed descriptively for the entire cohort and select subgroups. LOCF data imputation method will be used to impute responses to ASIS items # 9 & 10 for respective encounters for the Subjects with missing data at those encounters, prior to analyses.

Items from Expert Panel Questionnaire will be analyzed individually and CFB in individual questions/items will be reported for relevant categories of responses (depending on the response scales) descriptively. More detailed portrayal of this planned analysis will be outlined in the study SAP. No missing data imputation will be undertaken for these items.

#### **12.6.5 Comparison of Parent/Caregiver and Patient Perceptions of AV Severity and Impact**

Parent/caregiver and pediatric patient responses to the questions related to AV severity at Week 12 will be compared and reported using descriptive statistics, to portray the level of concordance/discordance in stakeholder perceptions, within the Subject age group of 12-17 yrs. This analysis will be conducted for the entire relevant cohort and for select subgroups, if sample size permits.

Responses to select Expert Panel Questionnaire items at Week 12 related to worries about Acne and impact of acne on child's lives will be compared to corresponding questions to parents/caregivers to portray the level of concordance/discordance in stakeholder perceptions, within the Subject age group of 12-17 yrs. This analysis will be conducted for the entire relevant cohort and for select subgroups, if sample size permits.

Parent/caregiver and pediatric patient responses to the questions at Week 12 related to the parents' understanding of child's concerns will be compared and reported using descriptive statistics, to portray the level of concordance/discordance in stakeholder perceptions, within the Subject age group of 12-17 yrs. This analysis will be conducted for the entire relevant cohort and for select subgroups, if sample size permits.

No missing data imputation will be undertaken for these items.

#### **12.6.6 Safety Assessments**

The safety data will be analyzed descriptively using Safety Population dataset (if it is different from FAS), to report the frequency of occurrences of AEs/ADRs and SAEs. These will be reported at individual item level as well in aggregate at specific category level (e.g., GI effects, vestibular effects) for each of the subject encounter timepoints (4, 8 & 12 weeks post-index date). The number of patients discontinuing treatment within the 3-month post-index date, and number of patients discontinuing the study within the entire study observation window (of 12 weeks) because of AEs/ADRs will be reported, as documented in patient medical charts.

#### **12.7 Missing Data Handling**

The missing data pertinent to the validated instrument ASIS will be handled per instrument owner instructions / scoring manual. For effectiveness measures obtained from Site Investigators and Subjects, namely, IGA, PtGA (from ASIS item # 9) and Patient appearance rating scale (from ASIS item # 10), LOCF data imputation method will be used to impute responses for Week 12 for the Subjects with missing data at Week 12. LOCF may also be used to impute responses for Weeks 4 & 8 for the Subjects with missing data at those encounters for

these select measures, as feasible. For all other study variables and endpoints, no missing data imputation is planned.

## 12.8 Sensitivity Analyses

Sensitivity analyses will explore the impact of missing data on the robustness of the results. Reasons for missing data and time to drop-out will be explored in a descriptive fashion. The key study outcomes will be explored for Subjects that completed the study versus those that discontinued the study, using descriptive statistics and multivariate regression models, as appropriate. If some Subject visits are conducted via remote visits instead of in-person visits, the nature of visit (remote vs. in-person) may be used to stratify the analysis of secondary endpoint involving IGA. The dataset with LOCF imputed values will be used to repeat only the select outcomes analyses as outlined in Section 12.7 and the results will be shown along with the results from analyses without LOCF data imputation.

Details of the sensitivity analyses will be described in SAP prior to database lock.

## 13 SOURCE DOCUMENTS AND ACCESS TO SOURCE DATA/DOCUMENTS

Study staff will maintain appropriate medical and research records for this study for the integrity of research and protection of confidentiality of Subjects. Study staff will permit authorized representatives of the IRB and study CRO to examine research records for the purposes of quality assurance reviews, audits, and evaluation of the study safety and progress.

The eDCFs represent a record of the subject's experience in the study, therefore, the eDCF data will be supported by original (or source) medical records, where feasible. Prior to enrolling a subject in the study, the Site Investigator or site staff will document his/her review of subject eligibility criteria in the source records for the subject. Current or changes in clinical characteristics of the AV patients, including current or changes to disease severity and medications will be documented in patient medical charts as part of routine clinical practice, and these may constitute source records for the Subjects. Data recorded directly into the eDCF (via online portal) is also considered source data when there are no other written or electronic records

preceding the eDCF entry; data from online surveys completed by study Subjects will be considered as source data, with no back-up records (or data copies) in patient medical charts.

No study monitoring visits will be conducted by the CRO as part of the study, as the sites and Subjects will be managed remotely, and all data will be collected using eDCFs. Occasional visits to select sites may be conducted (only as feasible) to monitor the progress of the study.

The electronically collected data will be periodically reviewed to evaluate the progress of the study; to verify the accuracy and completeness of eDCFs; to ensure that all protocol requirements, and Investigator's obligations are being fulfilled; and to resolve any inquiries related to the study data.

The Site Investigators agrees that the Study CRO or the IRB will have reasonable access to study source documentation (albeit, in de-identified manner) for purposes of audit both during and after completion of the study.

